9.0 OTHER ANALYSES

For each of the following outcome measures (CGI-I responder rate, PGI-I responder rate, IRLS total score, MOS-II score, MOS-I score, IRLS Question #7 score), data will be summarized for:

- Each of Arm 1 and Arm 2 at Week 24 for subjects assigned to each of NTX100 and Sham control in CT-04 Phase 1.
- Each of Arm 1 and Arm 2 at Week 24 compared to CT-05 study entry.
- Each of Arm 1 and Arm 2 at each of CT-04 study entry, CT-04 week 8, CT-05 week 8, CT-05 week 16, CT-05 week 24, [and CT-05 week 32 for Arm 1 only].

For CGI-I and PGI-I, data will be summarized for the proportion of subjects reporting any improvement, as measured by a response of 3 or lower (Minimally improved, Much improved, or Very much improved) and reported for each of Arm 1 Week 24, Arm 1 Week 32, and Arm 2 Week 24.

For MOS Sleep, data will be summarized and effect sizes will be presented for each Arm each of the following dimensions and items for each of CT-04 study entry and CT-05 week 24:

- MOS "Sleep disturbance" dimension (Items 07, 03, 08, 01)
- MOS "Somnolence" dimension (Items 09, 11, 06)
- MOS "Sleep adequacy" dimension (Items 04, 12)
- MOS "Quantity of sleep / Optimal sleep" dimension (Item 02)
- MOS Item 01 (Trouble falling asleep)

For each of the following components of SF-36, data will be summarized and effect sizes will be presented comparing Arm 1 of CT-05 study entry to Arm 1 CT-05 week 24 and comparing Arm 1 CT-05 week 24 to Arm 2 CT-05 week 24:

- Vitality
- Physical functioning
- Bodily pain
- General health perceptions
- Physical role functioning
- Emotional role functioning
- Social role functioning
- Mental health

Consent and completion rates will be presented for Arm 1.

Changes to RLS management: For subjects in each Arm, changes to RLS management will be presented including the following:

- Doctor visits for the management of RLS.
- New prescription medications added for the treatment of RLS.
- Prescription medications discontinued for the treatment of RLS.
- Increases to dosage of prescription medication for the treatment of RLS.

• Decreases to dosage of prescription medication for the treatment of RLS. For each, total numbers of subjects and percentages of subjects will be summarized by Arm from Week 1 to Week 24.

Exposure to treatment, completed sessions: For subjects in Arm 1, the total exposure to treatment will be summarized for Week 8 of CT-04 and Week 24 of CT-05 Arm 1 based on the following metrics. The rationale for these metrics is that subjects are instructed to only use devices on days with RLS symptoms.

- The average number and percentage of participants who completed a therapy session on a given day (Daily Active Participants, DAP) will be determined based on analysis of objective data from electronic device logs.
- The average number and percentage of participants who experienced RLS symptoms on a given day (Daily symptomatic participants, DSP) will be calculated based on IRLS Question #7, where responses 0, 1, 2, 3, 4 are mapped to 0, 1, 2.5, 4.5, 6.5 days/week respectively.
- The Objective Usage Rate (OUR) will be calculated by dividing the DAP by DSP for that week.

Exposure to treatment, therapy output intensity: For subjects in Arm 1, the therapy intensity level (in milliamps) will be summarized based on the following statistics:

- Calibrated therapy intensity level at entry to CT-04.
- Actual mean intensity value used at CT-04 Week 8, based on electronic device log data of completed sessions. Data will be averaged within subjects and then averaged across subjects.
- Actual mean intensity value used at CT-05 Arm 1 Week 24, based on electronic device log data of completed sessions. Data will be averaged within subjects and then averaged across subjects.

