16.1. Overview

Arms 1 and 3 involve a 24-week extension of in-home investigational device usage for subjects who previously completed the RESTFUL Study, followed by an 8-week period without investigational device usage to assess the progression of RLS following cessation of treatment. Two separate arms are employed to maximize the number of subjects eligible for any extension phase (Arm 1 and Arm 3) while also maximizing the number of subjects who can proceed directly to the extension phase (Arm 1 only). Notably, in the RESTFUL Study, subjects will have already completed either 4-weeks of device usage (Sham \rightarrow Active) or 8-weeks (Active \rightarrow Active) depending on randomization. Since site staff were blinded to RESTFUL Study treatment assignment, no procedures in this protocol will be affected by RESTFUL Study treatment assignment.

Arm 2 serves as a control arm with matched duration to the 24-week period of investigational device usage; this arm is designed to the assess the changes to medication and RLS symptoms that occur under the conventional standard of care, in the absence of investigational device intervention. Although the duration of Arm 2 states 24-weeks, each subjects participation will vary, since the 24-week period also includes the time between when the subject exits the RESTFUL study and when they enroll in Arm 2 of the CT-05 study. For example, subjects who are consented more than 8-wks after RESTFUL Study completion will only complete the remaining follow-ups (e.g. subjects consented 12-wks after the RESTFUL Study will only complete the 16-wk and 24-wk follow-ups).

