Evaluation 7: (20-wks after Eval #1) Phone follow-up to assess RLS symptoms, NTX100 use, and assess the occurrence of adverse events and/or changes to daily medications.

Evaluation 8: (24-wks after Eval #1) In-person follow-up to assess RLS symptoms, NTX100 use, and assess the occurrence of adverse events and/or changes to daily medications. Devices are returned at this time.

Evaluation 9: (32-wks after Eval #1) Phone follow-up to assess RLS symptoms, adverse events, and any changes to daily medications. Study exit occurs at this time.

* See Section 16.13 below for discussion of device replacement and in-person visits.

In addition to these assessments, subjects will complete a Weekly Questionnaire each week throughout the 24-wk duration of device usage and a Bi-weekly Questionnaire every 2-weeks from Weeks 25-32.

The schedule of assessments are shown in Table 4 below. Additionally, the devices may automatically log quantitative compliance, usage data, and leg movement data throughout the duration of the study.

Table 4. Schedule of Assessments for Arms 1 and 3

Investigational Plan, Protocol CT-05 (Extension Study)

Document #: CT-4

Rev: 1.0

Effective: 11/24/2021

		Eval 1 Day 0	Wks 1-24	Wks 25-32	Eval 2 Wk-2	Eval 3 Wk-4	Eval 4 Wk-8 In-person or	Eval 5 Wk-12	Eval 6 Wk-16 In-person or	Eval 7 Wk-20	Eval 8 Wk-24	Eval 9 Wk-32
		In-person	Remote	Remote	Remote	Remote	Remote**	Remote	Remote**	Remote	In-person	Remote
Assessment	Completed by											
Screening		X										
Consent		X										
Study entry												
questionnaire	Staff + subject	X										
Weekly questionnaire	Subject		X									
Biweekly questionnaire	Subject			X								
Review weekly												
questionnaire												
responses	Staff				X	Х	X	Х	X	Х	X	
ConMeds	Staff	X			X	X	X	Х	X	Х	X	X
AE Monitoring/Reporting	Staff				Х	Х	X	X	X	X	X	X
RLS	Staff + subject	X (Arm 3 only*)			X	X	X	X	X	Х	X	X
PGI-I	Staff + subject				X	Х	X	X	X	Х	X	X
CGI-I	Investigator + subje	ect					X		X		Х	X
MOS-Sleep	Staff + subject	X (Arm 3 only*)				X	X	Х	Х	Х	Х	X
SF-36	Staff + subject	X									Х	
Device completion												
questionnaire	Staff + subject										X	
Study exit questionnaire	Staff + subject											X
Device replacement Sta	Staff + subject	X **					X **		X **			
		* For Arm 1, data	from Eval	11 of the RE	STFUL Stu	dv will be	used, since bo	th Evals	typically occ	ur on the	same day	

Arm 2:

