16.16. Subject Discontinuation

A subject may be removed from the study prior to completion for any of the following reasons:

- Voluntary withdrawal of consent
- Adverse event preventing further study participation
- Investigator believes risk of further subject participation outweighs benefit
- Persistent non-compliance or lost to follow-up
- Pregnancy
- Subject no longer meets inclusion criteria
- [For arms 1 and 3 only] Subject makes a significant change to dosage of medications known to interfere with sleep or RLS symptoms, including sleep medications, antidepressants, sedative antihistamines.

Investigational Plan, Protocol CT-05 (Extension Study)

Document #: CT-4

Rev: 1.0

Effective: 11/24/2021

• [For arms 1 and 3 only] Insufficient device availability (see 16.16.1 below)

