3.2 Method of Assigning Subjects to Treatment

All subjects who are enrolled in Arm 1 will be assigned to:

- NTX100 programmed to ACTIVE mode for Weeks 1-24
- No treatment for Weeks 25-32

and will be instructed to maintain constant dosage and schedule of RLS medication (if applicable) for Week 1-32.

All subjects who are enrolled in Arm 2 will be assigned to:

• No treatment for Weeks 1-24 and will be permitted to change RLS medication during the study.

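### Week 32, the off-device result, is summarised without the drug changes and exits of Weeks 25-32, so a relapse treated with medication could be hidden in it

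*SAP*

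**What the plan says.** Protocol 16.1 describes 24 weeks of device use "followed by an 8-week period without investigational device usage to assess the progression of RLS following cessation of treatment". That is the only purpose given for the phase.

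Medication in the phase is addressed in three places. SAP 3.2 says that Arm 1 subjects "will be instructed to maintain constant dosage and schedule of RLS medication (if applicable) for Week 1-32". Protocol 16.12 defines Evaluation 9, at Week 32, as "Phone follow-up to assess RLS symptoms, adverse events, and any changes to daily medications. Study exit occurs at this time". Protocol 16.16 lists among the reasons for which an Arm 1 subject may be removed: "Subject makes a significant change to dosage of medications known to interfere with sleep or RLS symptoms".

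On analysis, SAP 9.0 limits the table of changes to RLS management (Table 2.18): "total numbers of subjects and percentages of subjects will be summarized by Arm from Week 1 to Week 24". For the main outcome measures, its list of by-visit summaries ends with "and CT-05 week 32 for Arm 1 only". The CGI-I and PGI-I any-improvement proportion is "reported for each of Arm 1 Week 24, Arm 1 Week 32, and Arm 2 Week 24". Both sets of tables (2.11 and 2.13) are in the ITT population. SAP 5.3 applies LOCF to missing efficacy endpoint data and does not say whether the Week 32 summaries are included.

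**The concern.** The off-device phase asks what happens to symptoms when stimulation stops. A Week 32 score answers that only if the reader knows whether something else replaced the device in the meantime. CGI-I is rated against baseline, which for Arm 1 is RESTFUL entry (Protocol 16.2 and 16.14), and nothing in the rating discounts a drug added or raised after Week 24. A subject who relapses, changes medication and then feels better can therefore score as improved at Week 32.

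A subject who relapses and leaves the study raises a different problem. On observed data, that subject drops out of the Week 32 figure. Under LOCF, the on-device Week 24 score could be carried into it. Either way, the figure could look more like persistence than the off-device course of the whole group. No primary or key secondary endpoint is touched; what is at stake is the stated purpose of one study phase.

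**Working it through.** The documents give no expected Week 32 result, no medication-change rate and no sample size (SAP 3.4), so there is no figure of the plan's own to reproduce. The check is a comparison of text, followed by an illustration on assumed inputs.

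**1. What is collected against what is summarised, Weeks 25-32, Arm 1**

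| Item | Collected | Planned output |
|---|---|---|
| RLS and sleep scores | Evaluations 8 and 9 | By-visit summaries (Table 2.11, ITT); by-subject listings 2.1-2.4 |
| CGI-I, PGI-I any improvement | Evaluations 8 and 9 | Table 2.13, ITT, Weeks 24 and 32 |
| Week 24 to 32 change within subject | Derivable from both visits | None |
| Medication changes | Evaluation 9 | Not tabulated after Week 24; by-subject listings 3 and 5.1 show no stated cut-off |
| Exits | Study exit form | Completion rates (Table 3.1) and listing 5.2, not tied to the Week 32 outcome |
| Adverse events | Evaluation 9 | Separate Week 25-32 proportion (SAP 8.3) |

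The SAP therefore treats Weeks 25-32 as a distinct period for adverse events but not for medication changes.

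**2. Do other populations close the gap?** The Stable Medication population (SAP 6.2) stops at Week 24 and serves only key secondary endpoints 6-11. The Per Protocol population excludes clinically significant RLS medication changes during the study, but it is built on evaluable Week 24 data, and the listed Week 32 tables are ITT. Neither qualifies the Week 32 figure.

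**3. Drug changes: illustration.** Let m be the share of Arm 1 who relapse and change medication in Weeks 25-32, and r the share of those who count as responders because of the drug. Upward shift in the Week 32 responder rate = m x r.

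| m | r = 25% | r = 50% | r = 75% |
|---|---|---|---|
| 0% | 0 | 0 | 0 |
| 5% | 1.25 points | 2.5 | 3.75 |
| 10% | 2.5 | 5 | 7.5 |
| 20% | 5 | 10 | 15 |
| 30% | 7.5 | 15 | 22.5 |

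For mean IRLS the shift is m x d, where d is the drug's relief in points. With d from 3 to 9, it is 0.05 x 3 = 0.15 to 0.05 x 9 = 0.45 points at m = 5%, and 0.9 to 2.7 points at m = 30%.

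**4. LOCF: illustration.** Let w be the share without a Week 32 score whose Week 24 value is carried forward, and x the IRLS points by which they would have returned off the device. Shift = w x x. At w = 10% and x = 3, 6 or 9, it is 0.3, 0.6 or 0.9 points; at w = 20%, it is 0.6, 1.2 or 1.8 points.

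Every value of m, r, d, w and x is an assumption.

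**The case against.** The case on the other side has real weight.

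- **Medication is meant to stay constant to Week 32.** If subjects comply, there is no masking. This stands as a limit on size. It does not remove the point, because the plan itself asks about changes at Evaluation 9 and allows removal for them.
- **Changes and exits are not invisible.** Listings 3, 5.1 and 5.2 and the completion table cover them, and a reader could match a late drug change to a Week 32 score by hand. This also stands: the accurate complaint is that they are listed but not summarised alongside the outcome. The table and listing shells are not in the supplied text, so their columns cannot be checked.
- **Week 32 is descriptive.** The primary and all 11 key secondary endpoints are at Week 24. A reader might infer that the plan will present drug-treated relapse as lasting benefit. The documents do not support that: no Week 32 hypothesis or claim is planned.
- **The by-visit summary already shows Weeks 24 and 32.** For the same subjects, the difference in means equals the mean paired change. What a paired analysis adds is a fixed set of subjects and a confidence interval.
- **Not every exit is a relapse.** Protocol 16.16 includes withdrawal of consent and pregnancy. Counting all leavers as failures would bias the result the other way, so the fix keeps them separate.

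A reader might also infer that leaving the Bi-weekly Questionnaire out of the SAP loses the key data. Its content is not given, so this cannot be shown.

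**Conclusion.** The gap is real but limited. The phase has a stated question and the data to address it, yet the planned summaries stop short of an answer: medication changes are tabulated only to Week 24, no Week 24 to 32 change is estimated, and the missing-data rule at Week 32 is unstated. A relapse treated by a drug change could be hidden in the Week 32 summary; that it will be cannot be said.

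The size is unknown. It is zero with no medication changes and no carried-forward values. Over the assumed range of 5% to 30% changers it runs from about 1 to 22.5 points on the responder rate, and the upper end requires many subjects to depart from the constant-medication instruction. No Week 24 conclusion is affected. The change is worth making because it is cheap and lets the phase answer its own question.

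**What to change.** Amend SAP 9.0, with a matching line in 5.3:

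1. Add a separate Week 25-32 column for Arm 1 to Table 2.18.
2. Report the within-subject Week 24 to Week 32 change in IRLS, MOS-II and MOS-I with a 95% CI, overall and in subjects with no RLS or sleep medication change through Week 32. Label the second group descriptive: it is selected on behaviour after the device stopped and may favour those who relapsed least.
3. Present Week 32 on observed data with no on-device value carried forward, and give the number of exits after Week 24 with reasons.
4. As a sensitivity summary only, repeat the Week 32 CGI-I and PGI-I responder rates with subjects who added or raised an RLS or sleep drug after Week 24 counted as not maintained. Show exits for unrelated reasons separately.

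The cost is SAP wording and a few table columns. Evaluations 8 and 9 and the study exit form already collect the data. The downside for the sponsor is that the Week 32 figure may be less favourable.

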17.4. Compliance

Compliance will be assessed during the first 24-wks of Arm 1 and Arm 3. Subjects will be instructed to use devices each nights that they report experiencing RLS symptoms. Therefore, percentage compliance with device usage will be calculated using the following formula:

100%*(nights of compliant use)/(total nights with patient-reported RLS symptoms)

Investigational Plan, Protocol CT-05 (Extension Study)

Document #: CT-4

Rev: 1.0

Effective: 11/24/2021

Nights of compliant use will be measured based on digital tracking of the timing and duration of
each NPNS device usage. In cases where digital tracking logs are incomplete or unavailable, the
data will not be included in the compliance analysis.

• A "night of compliant use" will be defined as a minimum of 25 minutes of active NPNS stimulation between noon and noon during an Assessment week.

 "Total assessment nights with RLS symptoms" will be defined as the total nights spent by all subjects in Assessment weeks when the subject reports RLS symptoms on the Weekly questionnaire.

 If a subject is discontinued from the study for reasons unrelated to subject response to treatment, compliance data will only be assessed up until the time of discontinuation. Such reasons could include lack of device availability, personal reasons, or adverse event unrelated to the study device.

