5.3 Handling of Dropouts and Missing Data

If there are any missing data for efficacy endpoints, the "Last Observation Carried Forward" imputation method will be used to impute the missing data. If no data are available in this study, then the last observation from CT-04 will be carried forward.

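### The SAP does not carry over the protocol's 24-week device-log compliance analysis; its only use-to-symptom ratio covers one of the 24 CT-05 device weeks

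*SAP*

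**What the plan says.** Both documents name adherence among the study objectives (Protocol 3; SAP 2.0). The protocol synopsis lists an adherence outcome measure, a ratio of days of use to days with symptoms, and Protocol 17.4 gives the detail:

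- Period: "Compliance will be assessed during the first 24-wks of Arm 1 and Arm 3".
- Numerator: nights of compliant use from digital tracking. Such a night "will be defined as a minimum of 25 minutes of active NPNS stimulation between noon and noon during an Assessment week".
- Denominator: nights on which the subject reports symptoms in the Weekly Questionnaire.
- Incomplete or unavailable logs: the "data will not be included in the compliance analysis".
- Discontinuation for reasons unrelated to response: "compliance data will only be assessed up until the time of discontinuation".

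SAP 9.0, under exposure to treatment, sets out a different calculation. It states that "the total exposure to treatment will be summarized for Week 8 of CT-04 and Week 24 of CT-05 Arm 1". Daily Active Participants (DAP) counts participants who completed a therapy session on a given day, from device logs. Daily Symptomatic Participants (DSP) comes from IRLS Question 7, "where responses 0, 1, 2, 3, 4 are mapped to 0, 1, 2.5, 4.5, 6.5 days/week respectively". Then: "The Objective Usage Rate (OUR) will be calculated by dividing the DAP by DSP for that week".

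SAP 3.5, which lists changes to protocol-specified analyses, does not mention compliance, adherence or Protocol 17.4. The SAP's list of tables contains one usage table (Table 3.2) and no compliance table.

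**The concern.** This is an extension study of longer-duration response, and adherence is addressed only through descriptive reporting. A reader of the SAP would expect the protocol's 24-week compliance percentage, or a statement that it has been replaced and why. The SAP gives neither. Instead it defines a usage ratio for a single CT-05 week.

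Two things are at stake. Adherence over Weeks 1–23 would go undescribed, although data for it are planned. And a Week 24 value could be read as the study's adherence result when it may lie well above or below adherence over the whole period. The value may also depend on how subjects without usable Week 24 logs are handled, which the available SAP text does not settle.

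**Working it through.** The plan gives no adherence figure to reproduce and SAP 3.4 makes no sample size determination, so the check is a comparison of the two definitions followed by simple proportions.

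**1. The two measures side by side**

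| Element | Protocol 17.4 | SAP 9.0 (OUR) |
|---|---|---|
| CT-05 period | first 24 weeks | Week 24 only |
| Use | at least 25 min stimulation in a night | a completed session, not defined in the SAP text |
| Symptoms | Weekly Questionnaire nights | mapped IRLS Question 7 categories |
| Missing logs | left out | no rule in the available text |
| Discontinuation | assessed up to that point if unrelated to response | no rule in the available text |

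OUR is also reported for CT-04 Week 8, but that is not a CT-05 week.

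**2. Coverage**

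1/24 weeks = 7/168 nights = 4.2% of the CT-05 device period.

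**3. Does another SAP section fill the gap?**

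No. Protocol 17.2.3 excluded from the per-protocol analysis subjects who used the device on fewer than two-thirds of symptom nights. The SAP's Per Protocol Population keeps only zero device uses as a usage criterion. SAP 3.5 does disclose that simplification.

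**4. How far one week can differ from 24**

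All usage patterns here are assumed. Symptom nights are held constant from week to week, and OUR is taken to equal the true ratio in Week 24.

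- Straight fall from 100% to 50%: the 24-week mean is (100 + 50)/2 = 75%; Week 24 gives 50%.
- 50% in Weeks 1–12, then 100%: (12 × 0.5 + 12 × 1)/24 = 75%; Week 24 gives 100%.
- 100% in Weeks 1–20, then 50%: (20 × 1 + 4 × 0.5)/24 = 91.7%; Week 24 gives 50%.

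The difference can go either way.

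**5. Missing logs**

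SAP 5.3 provides that, for efficacy endpoints, the last-observation-carried-forward "imputation method will be used to impute the missing data". IRLS Question 7 is an efficacy endpoint (SAP 4.2, endpoints 5 and 11); device logs are not. If carried-forward Question 7 values feed DSP, which is an inference, then DAP and DSP can rest on different subjects.

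A worst-case illustration assumes 100 subjects with 4.5 symptom days a week, full adherence, and 20% without Week 24 logs:

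- DSP = 100 × 4.5/7 = 64.3.
- DAP from the 80 subjects with logs = 80 × 4.5/7 = 51.4.
- From counts, OUR = 51.4/64.3 = 80%.
- From percentages, with DAP based on subjects with logs, OUR = 64.3/64.3 = 100%.

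SAP 9.0 reports both numbers and percentages and does not say which enters OUR.

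**6. Are the data planned?**

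Largely. Weekly Questionnaires run through all 24 device weeks (Protocol 16.12). Complete logs are not assured: automatic logging is described as something the devices may do, and log analysis at Evals 4 and 6 is not strictly required (both 16.12), while downloads at those visits are described only as typical (16.13).

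**The case against.** The strongest reply is that omission is not replacement. Protocol 17.4 is self-contained, with its own formula and rules. The protocol assigns the efficacy analysis to the SAP and allows it to add safety plans, but never assigns compliance to it. SAP 1.0 describes the document as covering efficacy and safety. The SAP section is about exposure and nowhere says that OUR supersedes compliance, and SAP 3.5 has a general sentence on further modifications outside the primary and key secondary endpoints. This stands to the extent that one cannot say 17.4 was withdrawn. It does not remove the gap: the SAP keeps adherence as an objective, defines a different use-to-symptom ratio and does not point to 17.4, so whoever programs from it would produce Week 24 only.

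Other points also stand:

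- The shells for Table 3.2 and Listing 5.3 are not in the available text and may state denominators or a missing-log convention. The two-week restriction, however, is in the SAP text itself.
- A session may run about 30 minutes (Protocol 16.9), so a completed session would usually pass the 25-minute threshold; that difference is probably small.
- The usage patterns in the working are constructed. They show what is possible, not what is expected.
- The missing-log figures need a mismatch that no section prescribes.

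A reader might also infer that the Question 7 mapping seriously distorts OUR, since at full adherence an individual's ratio could run from 80% to 120% (2/2.5 and 3/2.5, if a score of 2 spans two to three days). The documents do not support that as an error in the result: OUR divides two group averages, individual ratios are not reported, and such deviations partly cancel.

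**Conclusion.** The point holds as a gap between protocol and SAP. The SAP as written covers 1 of 24 CT-05 device weeks, does not cite or carry over the protocol's 24-week compliance analysis, and does not record the change. A Week 24 ratio may over- or understate 24-week adherence; under the assumed straight fall from 100% to 50%, it is 25 percentage points too low (50% against 75%). The actual size cannot be known from the documents.

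Three stronger readings go too far. One is that the sponsor dropped the adherence analysis: 17.4 was never formally withdrawn, and OUR is itself a partial, log-based substitute. Another is that no missing-log rule exists anywhere: that can be claimed only for the text available. The third is that the study's efficacy conclusions are weakened: adherence is neither a primary nor a key secondary endpoint, and no hypothesis test or type I error rate is affected. What is limited is what can be concluded on the adherence objective.

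**What to change.** Add the Protocol 17.4 compliance percentage for Arm 1 over Weeks 1–24 to SAP 9.0, using the device logs and Weekly Questionnaires. Carry over the protocol's rules for incomplete logs and for discontinuation unrelated to response. Because complete logs are not assured, report the number of subjects and weeks excluded for missing logs.

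Keep OUR as a supplementary Week 24 index, with DAP and DSP computed on the same subjects. State how missing logs are treated and whether counts or percentages are used. Record the change in SAP 3.5. If the intention is that 17.4 applies unchanged alongside OUR, say so explicitly.

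Optional drafting improvements are to define the term Assessment week, which 17.4 uses without definition, to add a rule for discontinuation related to response, and to show compliance in 4-week blocks.

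The cost is a SAP edit and some extra programming, with no new visits. The adherence figure may turn out less favourable than the Week 24 ratio, and some subject-weeks will be lost to missing logs.

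### The Objective Usage Rate in SAP 9.0 is a crude group usage ratio: it can exceed 100%, can rise as symptoms fall, and can hide untreated symptom days, so it should not stand for adherence

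*SAP*

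**What the plan says.** Adherence is part of the study objective (Protocol 3, SAP 2.0). The Protocol Synopsis defines the adherence outcome as days of device use over days with RLS symptoms.

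Protocol 17.4 gives a compliance formula for the first 24 weeks, "100%*(nights of compliant use)/(total nights with patient-reported RLS symptoms"), with these features:
- Symptom nights come from the Weekly Questionnaire and are totalled over all subjects.
- A compliant night needs a "minimum of 25 minutes of active NPNS stimulation between noon and noon during an Assessment week".
- Data with incomplete or unavailable device logs are left out.
- The numerator is not restricted to nights with symptoms.

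SAP 9.0, under exposure to treatment, uses different quantities, "summarized for Week 8 of CT-04 and Week 24 of CT-05 Arm 1":
- Numerator: "The average number and percentage of participants who completed a therapy session on a given day (Daily Active Participants, DAP"), taken from device logs.
- Denominator: "The average number and percentage of participants who experienced RLS symptoms on a given day (Daily symptomatic participants, DSP"), taken from IRLS Question 7, "where responses 0, 1, 2, 3, 4 are mapped to 0, 1, 2.5, 4.5, 6.5 days/week respectively".
- Ratio: "The Objective Usage Rate (OUR) will be calculated by dividing the DAP by DSP for that week".

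The reason given is that "subjects are instructed to only use devices on days with RLS symptoms". SAP 9.0 states no cap on OUR and no link between a subject's use and that subject's symptom days. It repeats none of the Protocol 17.4 features listed above for OUR.

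**The concern.** The rationale is about use on symptom days, but nothing in the ratio identifies use on symptom days. A completed session counts whether or not the subject had symptoms that day. Symptom frequency enters only as a separate group average from one weekly recall item.

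That item, scored on treatment, is also the basis of key secondary endpoint 5. A successful device shrinks the denominator, so a change in OUR between CT-04 Week 8 and CT-05 Week 24 may reflect symptoms, use, or both.

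At stake is how the adherence objective is reported. No other SAP figure sets use against symptoms, so OUR is likely to be read as the adherence result despite its exposure heading.

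**Working it through.** The documents give no OUR value, so there is none to reproduce. What follows is arithmetic on the SAP definition. The use patterns are assumptions.

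**Formula.** With the same N subjects in both terms, OUR = (total use days / 7N) / (total mapped Question 7 days / 7N) = mean use days / mean mapped symptom days. The mapped values are 0, 1, 2.5, 4.5 and 6.5.

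**1. Values above 100%.** If every subject scores 4 on Question 7 and uses the device on 7 days, OUR = 7/6.5 = 107.7%.

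The midpoints alone shift the result. Assume, as they imply, that scores 2, 3 and 4 mean 2-3, 4-5 and 6-7 days. Use on every symptom day and no other then gives:
- score 2: 2/2.5 = 80% to 3/2.5 = 120%
- score 3: 4/4.5 = 88.9% to 5/4.5 = 111.1%
- score 4: 6/6.5 = 92.3% to 7/6.5 = 107.7%

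**2. Rise as symptoms fall.** Hold mean use at 5 days a week and let mean mapped symptom days fall from 6 to 4. Both means are reachable: 0.75 × 6.5 + 0.25 × 4.5 = 6, and 0.75 × 4.5 + 0.25 × 2.5 = 4. OUR goes from 5/6 = 83% to 5/4 = 125%.

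OUR can rise even while use falls. Use of 5.5 days with everyone at score 4 gives 5.5/6.5 = 84.6%. Use of 4.0 days with half at score 3 and half at score 2 gives 4.0/3.5 = 114.3%.

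**3. Masking between subjects.** Take ten subjects, all at score 2. Five use the device on 0 days and five on 5 days.
- OUR = (5 × 0 + 5 × 5) / (10 × 2.5) = 25/25 = 100%.
- Mapped symptom days treated, at most: (5 × 0 + 5 × 2.5) / 25 = 12.5/25 = 50%.

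**4. Counter-check.** If every subject's use is 80% of mapped symptom days, OUR is 80% at every symptom level: 5.2/6.5, 3.6/4.5 and 2.0/2.5. The rise in step 2 therefore needs use that does not fall in step with symptoms.

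**5. Would capping on Question 7 days repair it?** Take fully adherent subjects split evenly within a category, and cap use at the mapped days.
- Score 2: (2/2.5 + 2.5/2.5)/2 = 90%.
- Score 4: (6/6.5 + 6.5/6.5)/2 = 96.2%.

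Uncapped, each pair averages 100%, so a cap on mapped days adds a downward bias. In the constant-use case of step 2, taken as a single subject, the capped rate still moves, from 5/6 = 83% to 4/4 = 100%. A capped rate is only an upper bound. Only matching by night resolves this.

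**The case against.** The strongest reply is that OUR is the aggregate form of the protocol's own adherence ratio, and that subjects are told to use the device only on symptom days. If they do, OUR is the pooled share of symptom days treated, apart from midpoint error. The SAP calls it exposure, tests nothing on it, and reports DAP and DSP beside it, so a reader can see whether use or symptoms moved. Listing 5.3 is also planned for usage.

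Much of this stands. Showing DAP and DSP largely answers the mixing of use with efficacy. It does not answer the masking in step 3, because two group averages cannot show who treated which days, and SAP 9.0 plans no subject-level rate.

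A reader might infer more than the documents support:
- **That OUR does not measure adherence at all.** It is a crude group proxy, sound to the extent that use is confined to symptom days.
- **That group averaging causes all the defects.** A per-subject ratio with the same numerator and mapping would also exceed 100% and rise as symptoms fall. Group averaging causes only the masking.
- **That one night's use will count as two days.** SAP 9.0 does not define a day. A midnight boundary would be read into that silence, and Protocol 17.4 specifies noon to noon.
- **That only the SAP has the problem.** The Protocol 17.4 formula is also pooled, uncapped and open to use on nights without symptoms.

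**Conclusion.** The point holds in a limited form. OUR can exceed 100% (107.7% for daily use at score 4), can move from 83% to 125% with no change in use, and can read 100% when at most 50% of mapped symptom days were treated. These cases show what the definition permits. They do not predict what the trial will report, and the documents give no data on use outside symptom days. If use stays proportional to symptoms, OUR is stable.

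The results assume the same subjects in numerator and denominator; the within-category figures also assume that the midpoints stand for the day ranges in step 1. The effect is confined to a descriptive output. It is worth correcting because adherence is a stated objective and the protocol already specifies a better source for symptom nights.

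**What to change.** In SAP 9.0, add a per-subject adherence rate for Arm 1 over CT-05 Weeks 1-24, built on Protocol 17.4: Weekly Questionnaire symptom nights, at least 25 minutes of logged use, noon to noon, incomplete logs excluded.

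- Where the questionnaire identifies individual nights, count only use on symptom nights. The documents do not show the questionnaire, so whether it does must be checked.
- Otherwise, cap each subject-week's use nights at that subject's reported symptom nights and label the result an upper bound. Do not apply the cap to Question 7 mapped days.
- Show the distribution across subjects. Leave subject-weeks with no symptom nights out of the rate and report how many there were, since leaving them out removes the weeks of best response.
- Apply the same symptom-night limit to the Protocol 17.4 numerator.
- Keep DAP and DSP as descriptive exposure, computed on the same subjects. Label OUR as a group usage ratio that can exceed 100% and is not symptom-night adherence.

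The logs and questionnaires are already planned, so the cost is SAP wording and a little programming. The reported adherence figure will probably be lower.
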